### Study groups

*Group 1:* Screening using biennial FIT (latex agglutination, OC-Sensor®, cut-off point: 75 ng Hb/ml), and performance of colonoscopy in patients with a positive result.

*Group 2:* Screening using one-time colonoscopy.

The study design allowed for cross-over between both screening strategies.

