### Sample size calculation

With an alpha risk of 0.025 and a beta risk of 0.20, using one-sided test of proportions, 27,749 subjects are required in each trial arm (total: 55,498) accepting a non-inferiority condition if the absolute difference was below 1.6% in the CRC-specific mortality rate at 10 years according to the intention to screen analysis (primary objective of the study).

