#### 4.5. Sample size calculation

##### Considerations for calculation of the sample

Since there are no study examining the effect of screening with the strategies proposed in our trial on CRC-caused mortality, the calculation of the sample in this case must be based on hypothetical studies of cost-effectiveness that analyse the expected reduction in risk of mortality with biennial FIT or colonoscopy every 10 years. Furthermore, the calculation should be adjusted, when possible, to the local conditions where the strategies are to be implemented. In that sense, it is important to note that no study on this subject have yet been published in Spain.

Recently, the Evaluation and Planning Unit of the Canary Islands Health Service has conducted a study of this type based on real data for sensitivity and specificity of the tests in our setting. For a hypothetical population of 100,000 asymptomatic individuals aged 50, the estimated mortality reduction brought about by FIT is 51% and involves a cost of € 2,101/QALY. For the strategy of colonoscopy, the estimate is a reduction in mortality of 75% at a cost of € 2,188/QALY.

With an alpha risk of 0.025 and a beta risk of 0.10 using one-sided test of proportions, 27,749 subjects are required in each arm of the clinical trial (total: 55,498) accepting a non-inferiority condition if the absolute difference was below 1.6% in the CRC-specific mortality rate at 10 years according to the intention to screen analysis and with an expected overall compliance of 30%.

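### The 1.6-point non-inferiority margin is too wide for any plausible 10-year CRC death rate to be informative, and it does not reproduce the stated sample size

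*Combined protocol and SAP*

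**What the plan says.** The executive summary and section 4.5 give the same acceptance rule, an absolute difference in 10-year CRC mortality. Section 4.5 has "accepting a non-inferiority condition if the absolute difference was below 1.6% in the CRC-specific mortality rate at 10 years according to the intention to screen"; the summary words it the same way. Section 4.5 gives the size as "27,749 subjects are required in each arm of the clinical trial (total: 55,498") and adds "with an expected overall compliance of 30"%. It takes its effects from a cost-effectiveness model: a 51% mortality reduction for FIT and, for the other arm, "For the strategy of colonoscopy, the estimate is a reduction in mortality of 75"%.

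The two places disagree on power for the same N. Section 4.5 has "With an alpha risk of 0.025 and a beta risk of 0.10 using one-sided test of proportions"; the summary has "With an alpha risk of 0.025 and a beta risk of 0.20, using one-sided test of proportions".

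The summary also notes that "The study design allowed for cross-over between both screening strategies". Section 4.4 qualifies this: the alternative test is available on request and is not actively offered. No cross-over rate is given.

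Section 7 plans 10-year risk differences and risk ratios with 95% confidence intervals, by intention-to-screen, as-screened and per-protocol. It does not restate the margin. Nowhere do the documents give an expected 10-year CRC death risk in either arm, or a justification for 1.6%.

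**The concern.** A non-inferiority margin is useful only if a clearly worse treatment could fail it. Death from CRC within 10 years is uncommon in an average-risk population aged 50 to 69, and an absolute margin of 1.6 points may exceed the whole risk that screening could remove. If so, a FIT programme that prevented no deaths would still be declared non-inferior to colonoscopy. The design is labelled non-inferiority, and this sentence is its only acceptance rule, so a headline claim of non-inferiority would say nothing about whether FIT works.

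**Working it through.** **Inputs.** From section 4.5: n = 27,749 per arm, one-sided alpha 0.025, margin 1.6 points, compliance 30%, reductions of 51% and 75%. Beta is 0.10 (section 4.5) or 0.20 (executive summary). R, the 10-year CRC death risk without screening, is not given. I assume 0.3% to 1.5% and extend to 3% as a stress test. Compliance is taken as 30% in each arm. Non-inferiority is taken to mean that the upper 95% limit of FIT minus colonoscopy lies below the margin.

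**1. Can the stated N be reproduced?** With no true difference and event risk p in both arms, n = 2(z_alpha + z_beta)² p(1−p) / margin².

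- Margin 1.6 points, no compliance adjustment: n is largest at p = 50%, at 15,330 per arm (beta 0.20) or 20,523 (beta 0.10). Neither reaches 27,749. At p = 1%, n is only 608 or 813.
- N inflated by 1/0.30: 27,749 requires p of about 16% (beta 0.20) or 11% (beta 0.10).
- Margin diluted to 0.30 × 1.6 = 0.48 points: 27,749 requires p of about 4.3% or 3.1%.
- Margin 0.16 points, no adjustment: p(1−p) = 27,749 × 0.0016² / [2(1.96 + z_beta)²], giving p = 0.45% (beta 0.20) or 0.34% (beta 0.10).

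So 1.6 points yields the stated N only with an undocumented compliance adjustment and a death risk of about 3% to 16%.

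**2. What difference do the plan's inputs imply?** Arm risk = R × (1 − uptake × reduction).

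- Modelled effects, 30% uptake: 0.30 × (0.75 − 0.51) = 7.2% of R. A 1.6-point difference needs R = 0.016/0.072 = 22%.
- FIT with no effect, 30% uptake: 0.30 × 0.75 = 22.5% of R, so R = 0.016/0.225 = 7.1%.
- Modelled effects, full uptake: 0.75 − 0.51 = 24% of R, so R = 0.016/0.24 = 6.7%.

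Cross-over shrinks the difference only modestly. If 20% of colonoscopy-arm participants took FIT instead, 7.2% would become 0.30 × (0.8 × 0.75 + 0.2 × 0.51 − 0.51) = 5.8% of R.

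**3. How often would a FIT with no effect pass?** At 30% uptake, SE = √[p_F(1−p_F)/n + p_C(1−p_C)/n], and the probability of passing is Φ[(0.016 − difference)/SE − 1.96].

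| R | FIT risk | Colonoscopy risk | Difference (points) | Expected upper 95% limit (points) | P(declared non-inferior) |
|---|---|---|---|---|---|
| 0.3% | 0.300% | 0.233% | 0.07 | 0.15 | 1.00 |
| 0.5% | 0.500% | 0.388% | 0.11 | 0.22 | 1.00 |
| 1.0% | 1.000% | 0.775% | 0.23 | 0.38 | 1.00 |
| 1.5% | 1.500% | 1.163% | 0.34 | 0.53 | 1.00 |
| 3.0% | 3.000% | 2.325% | 0.68 | 0.94 | above 0.99999 |

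**4. What remains informative?** Under the modelled effects at 30% uptake, the 95% half-width for the risk difference is about 0.11 points at R = 0.5% and 0.18 at R = 1.5%. On the ratio scale R cancels: a FIT with no effect gives 1/(1 − 0.225) = 1.29, and the modelled effects give (1 − 0.153)/(1 − 0.225) = 0.847/0.775 = 1.09.

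**The case against.** Several stronger readings are tempting, and the documents do not support them.

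- *The trial cannot answer its primary objective.* The objective in section 3.1 is to compare 10-year CRC mortality, and section 7 plans the risk difference and risk ratio with intervals. Only the pass/fail verdict is empty. The as-screened and per-protocol analyses add information, though they carry no stated margin.
- *Low uptake and free cross-over are the cause.* Cross-over is on request only. With the modelled effects at full uptake, R would still have to be 6.7%. Uptake and cross-over add to the problem; the root is the size of the margin against the event rate.
- *The margin can never be failed.* That depends on R, which is not stated, and on the scenario. With full uptake and R = 2%, a FIT with no effect would fail about 82% of the time. Under the plan's own 30% uptake, the finding holds throughout 0.3% to 3%.
- *7.2% of R is a ceiling.* It assumes equal uptake. At an illustrative 20% for FIT and 40% for colonoscopy, the difference is 0.40 × 0.75 − 0.20 × 0.51 = 19.8% of R, and 1.6 points would need R = 8.1%. The margin is still too wide.
- *No event rate fits 1.6 points.* That is true only if the stated compliance is ignored.
- *The margin must have been 0.16 points.* The fit to N is suggestive, but the documents cannot confirm it. Nor is 0.16 a reliable discriminator: at R = 0.3% a FIT with no effect passes 56% of the time; at R = 0.5% it passes 13% and the modelled effects 63%; at R = 1% the modelled effects pass only 21%.

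Timing also matters. Section 8 places study completion in December 2021 and the main analysis in June 2024, so choosing a new margin now would be a post hoc change to the decision rule, even if the new one were stricter.

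**Conclusion.** The concern stands in this form: the 1.6-point rule, as written, carries no information about non-inferiority. At 27,749 per arm and 30% uptake, a FIT that prevents no deaths would meet it with probability about 1.00 for any R from 0.3% to 1.5%, and above 0.99999 at 3%. This rests on an assumed R, equal uptake in both arms, the 75% colonoscopy effect and the normal approximation. The wide distance between the assumed risks and the 7.1% needed makes it insensitive to moderate changes in these. Separately, the sample size statement is not reproducible as written, and its beta differs between the two places. A decimal slip is a reasonable hypothesis, not a finding. The point requires correction because the rule is the sole basis for a non-inferiority claim.

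**What to change.** Check the original sample size calculation. In the executive summary and section 4.5, state the assumed control rate, how the 30% compliance entered, and whether beta is 0.10 or 0.20.

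- If the records show that 1.6 per 1,000 was meant, correct the margin in both places and cite that record. Show its operating characteristics at the stated control rate.
- If 1.6 points was meant, draw no non-inferiority conclusion from it and do not choose a new margin after the data. Base the conclusion on the planned intention-to-screen 10-year risk difference and risk ratio with 95% confidence intervals. Read the ratio against about 1.29, the value for a FIT with no effect at 30% uptake and a 75% colonoscopy reduction.

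The cost is a search of the trial records and revised text, with no new patients or data. The downside for the sponsor is that the criterion becomes stricter or the non-inferiority claim is dropped.

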#### Estimates of recruitment by Autonomous Region

According to the established sample size, the number of individuals to be recruited in each Autonomous Region is 6,937.

#### **4.6. Processes of selecting and inviting the population to be screened**

In each Autonomous Region, randomisation will be done prior to sending the invitation letter (Zelen's design) in order to properly assess the participation in each screening group and perform the intention to screen analysis of the results.

The selection process will be the same as the one used in the Nottingham study (14), in which compliance with the programme reached 60%. Briefly, target population will be identified from the Community Health Registry (CHR) of each Autonomous Region. The CHR is based on the population registry, and includes unique identification for each person, such as name, date of birth, social security number, and contact address, and it is updated regularly to account for population migration, deaths and changes in personal details. This list will be refined using cancer registries or other sources of information (primary care medical records, hospital databases, etc.) in order to eliminate individuals who meet exclusion criteria (i.e. CRC and colorectal adenoma) or who have died. Prior to randomisation, individuals will be clustered by household. With such an approach, it is hoped to ensure that all individuals in one household will be assigned to the same study group.

All individuals will receive an initial, pre-invitation letter by mail (which may be signed by their primary care doctor or an area specialist, or the person responsible for the Autonomous Regions screening programme) with information regarding the relevance of CRC as a health problem, the possibility of preventing it by means of screening, and the impending start up of a pilot programme (**presentation letter**), along with an informative leaflet which explains existing measures for CRC prevention. They will later be sent a second letter (also signed by their primary care doctor or area specialist, or the person responsible for the Autonomous Regions screening programme) in which they are invited to participate in the study (**invitation letter**) and includes an appointment to the Local Screening Office (LSO) and a contact telephone number. In the invitation letter, individuals will also be informed of the screening option that applies to them, the characteristics of the test and its possible adverse effects. This whole process will be performed by the LSO (who may be assisted by staff of the project data manager).

Individuals who do not respond will receive a **reminding letter** at 3-4 months after sending of the introduction letter. Individuals who do not respond to it will receive a second reminding letter 2 months later.

The content of the two letters will be identical in all Autonomous Regions. However, translation into official languages and the use of logos, institutional images or letterheads of each Autonomous Regions is permitted.

The frequency of sending invitation letters will be adapted to the capacity of each LSO to attend individuals wishing to participate in order to diminish the lag time between randomisation and participation to less than 3 weeks.

At the Health Centre, the functions of staff responsible for the study (including physicians and nurses of the centre and the data-collector in charge of the study) will be: 1) To track selected individuals in the sample who do not respond or who do not come to the appointment; 2) For those who come to the appointment, to confirm their suitability to participate in the study (compliance with inclusion/exclusion criteria); 3) To provide more detailed and exhaustive information about the study objective and the strategy they have been assigned in order to facilitate their participation; 4) To identify high-risk individuals, and assign them an appointment for a high-risk clinic of the reference hospital or the corresponding genetic counselling unit (see below); 5) To obtain written informed consent for participation in the study; 6) To complete the questionnaire with the data of all individuals contacted and include them in the project database; and 7) To provide a FIT kit (Group 1) or formalise the appointment at the hospital CRC prevention unit assigned to perform the colonoscopy (Group 2). In the event that an attending individual refuses to participate in the study, the baseline questionnaire will be completed and the reasons for the refusal of the invitation will be recorded. They will also be informed that even if they are not examined during screening, they will be contacted periodically in order to monitor the state of their health.

#### **4.7. Determination of faecal occult blood**

Reading of the FIT tests will be done in a centralised manner in each Autonomous Regions.

At the baseline round, individuals participating in the FIT arm will be advised of returning the completed kit to the LSO within 5 working days and maintaining it in their refrigerator until such a moment. From the LSO to the centralized laboratory kits will be transported in insulated cooler bags once a day. On subsequent screening rounds, logistics for delivering and returning FIT kits will be adapted to the one employed in each Autonomous Region (i.e. in person on primary care centres or pharmacies without previous appointment, or by mail).

#### **4.8. Technical characteristics of colonoscopies**

All colonoscopies performed in a screening programme must be of the highest quality to avoid false negative results and to minimize potential complications. Results of colonoscopy will determine the interval until next endoscopic examination, which is 10 years if no neoplastic lesions are detected, according to current recommendations. Colonoscopies will be performed by experienced staff in the centres involved in the study, which should be able to make correct diagnoses and carry out proper treatment of different types of neoplastic lesions. In addition, these examinations will be performed in specific work modules with sufficient resources to offer the quality required. In that sense, it is important to keep in mind that more than half of the examinations performed to confirm a positive FIT are associated with a therapeutic procedure, most often polypectomy.

The period of time between acceptance to participate and performance of colonoscopy in individuals allocated to colonoscopy (Group 2) or between a positive

FIT result and performance of colonoscopy in individuals allocated to FIT (Group 1) will be established in less than one month.

Endoscopic procedures will be recorded in the appropriate databases, including high quality digital photographs of all lesions detected. The report should contain the parameters for quality assessment (caecal intubation, insertion and withdrawal times, quality of cleanliness for each colorectal segment, number of polyps identified, removed and recovered for histological examination, retroflexion manoeuvre in the rectum, immediate complications, etc.).

Proper cleansing should be another pillar of colonoscopy in the screening programme. Whichever method is used, part of the preparation should be administered a few hours before the procedure, since in various studies this pattern has resulted in, not only better quality cleansing, but also a greater proportion of patients with polyps detected. Any of the commercially available methods can be used (polyethylene glycol [Bohm® solution] or disodium hydrogen phosphate [Fosfosa®]), whether combined or not with bisacodyl (Dulco Laxo®), taking care to provide the last dose for cleansing as close to the time of the colonoscopy as possible.

All colonoscopies will be performed under sedation.

In patients treated with anti-platelet agents, both for those in Group 1 with a positive FIT test (positive predictive value for colorectal neoplasia greater than 40%) and in Group 2 (positive predictive value of 5-7%), withdrawal or changes in medication will be assessed 7-10 days before testing. However, it is important to note that, according to current scientific recommendations, it is not necessary to discontinue anti-platelet agents to perform a polypectomy. Anti-coagulated patients (dicoumarol) should be changed, when possible, to subcutaneous administration of LMW heparin. Finally, the usefulness of metal clips has been described for the prophylaxis and treatment of post-polypectomy bleeding in at-risk groups, including in anti-coagulated patients.

The American Heart Association does not recommend the use of antibiotics prior to completion of endoscopic procedures (including colonoscopy and polypectomy) for prophylaxis of infectious endocarditis (<http://circ.ahajournals.org/cgi/reprint/CIRCULATIONAHA.106.183095>).

Biopsy of the polyp will be sought before polypectomy, especially for patients in whom it is anticipated that it will be difficult to obtain after the procedure. This measure aims to reduce the number of polyps not histologically studied.

In cases where colon cleansing is not adequate, the colonoscopy will be repeated.

In cases of failure to achieve complete colonoscopy, the procedure will be repeated or a CT-colonography will be offered.

Quality standards will be established for all the above requirements according to the recommendations made by the Quality Assurance Task Group of the National Colorectal Cancer Roundtable (44), which shall be subject to internal auditing during the course of the study. This will be the responsibility of the Quality Committee created specifically for this purpose (see below).

#### **4.9. Quality assurance programme**

A specific program will be designed to assure the quality of the whole process. It will include the following measures:

- A communication plan based in a comprehensive informative campaign designed and launched by the Spanish Alliance for CRC Prevention involving national and local media.
- Data will be registered in a centralized, safe database accessible online ([www.coloncrib.org](http://www.coloncrib.org)).
- Quality of FIT measurements will be assured by daily calibration at each reference laboratory, and external validation with samples provided by the manufacturer every 6 months.
- Colonoscopy quality will be ensured following the guidelines of the Spanish Gastroenterological Association and the Spanish Society for Digestive Endoscopy.

A specific **Quality Committee** will be created to oversee the quality assurance programme all over the study. This committee will meet in a periodical basis and will monitor by means of periodic audits the three main phases of the study (recruitment process, FIT determinations and colonoscopy).

## 5. DEVELOPMENT OF THE STUDY

This research project is included within the population-based screening programme of each Autonomous Region. This screening programme will ensure the recall of individuals for appointments in successive rounds of screening, while also continuing the strategy assigned to them during the randomisation of the study. The investigators will also be responsible to electronically or manually transfer to the LSO the information derived from the study that is of interest to the population screening programme.

Each Autonomous Region is committed with recruiting the same number of individuals regardless of the number of participating health centres or hospitals in each region.

The dynamics of the study are summarised as follow:

- Participants in Group 1 with a negative FIT will remain in their assigned group and will be offered the next round of screening at 2-year intervals until the age of 69. All of them will be sent a letter informing them of the test result and the date of the next round of screening. Individuals who enter the study at the age of 68 or 69 will undergo a single round of screening.
- Participants in Group 1 with a positive FIT will be contacted by phone and sent a letter informing them of the test result and the date of their appointment with the primary care physician (or specialist) or the person responsible for the screening programme, depending on the Autonomous Region. They may be assisted in this task by the project staff. During the visit they will be informed about the colonoscopy procedure and will be scheduled for this procedure.
- Participants in Group 1 with a positive FIT but who have normal colonoscopies or in whom only non-neoplastic disease is detected will remain in the FIT arm and will be offered the next round of screening using the biennial FOBT test at 10 years after performance of the colonoscopy.
- Participants in Group 2 who are found to be negative in colonoscopy or in whom only non-neoplastic disease is detected, will remain in the colonoscopy arm and will be offered a new colonoscopy at 10 years after performance of the baseline colonoscopy.

Surveillance colonoscopy for patients with adenomas will be carried out according to the Joint Guideline from the *US Multi-Society Task Force (USMTF)* (45).

- Participants in either Group 1 or Group 2 in whom only 1 or 2 non-advanced adenomas (low-risk adenomas) are detected, will be included in a surveillance programme and offered a new colonoscopy at 5 years.
- Participants in either Group 1 or Group 2 in whom 3 or more non-advanced adenomas or 1 or more advanced adenomas (high-risk adenomas) are detected will be included in a surveillance programme and offered a new colonoscopy after 3 years.
- Participants in either Group 1 or Group 2 in whom >10 adenomas are detected in a single examination will be scheduled for surveillance colonoscopy in less than 3 years.
- Participants in either Group 1 or Group 2 in whom a large sessile adenoma is detected and removed by piecemeal resection will undergo a colonoscopy in 2-6 months to verify complete removal.

- The interval between subsequent surveillance colonoscopies will depend on the findings of the earlier examinations. In general, if a neoplastic lesion is detected, the above-mentioned criteria will be applied. On the other hand, if the examination is normal or if only non-neoplastic disease is detected, the next colonoscopy will be performed 5 years later.
- For participants in either Group 1 or Group 2 in whom a malignant polyp is detected (pT1N0M0) and for whom endoscopic polypectomy is deemed sufficient (see criteria below), a new colonoscopy will be performed with biopsy of the resected area within a period of no more than 2-3 months to confirm that complete resection of the lesion was achieved. Subsequently, new colonoscopies will be performed after 1 and 3 years.
- Participants in either Group 1 or Group 2 in whom an invasive CRC is detected will be treated and followed up according to the specific protocol of each centre, but always including a colonoscopy 1 year after the resection, and every 3 years thereafter.

Any individual may refuse the screening examination assigned and request an alternative method. Any such individual will be assessed according to the group to which he/she was randomised for the “intention to screen” analysis, and according to the procedure actually performed in the “as-screened” analysis. These same criteria will be applied when any screening examination is performed (FOBT, colonoscopy, CT-colonography, or colonic capsule) and that is not foreseen in the study, regardless of the reason.

All randomised subjects, whether the appropriate screening strategies have been performed or not, will be followed up for the purpose of tracking changes in the state of their health.

Individuals who are not contacted will be registered for calculation of the invited population.

For subsequent screening rounds, the same system of invitation will be used and according to each Autonomous Region policy.

The CRC prevention units will ensure the performance of colonoscopies no more than 4 weeks after the procedure is indicated. Patients in whom any neoplastic colorectal lesion is detected will be treated and followed up properly.

The treatment of lesions detected in any screening examination will be conducted according to the specific protocol of each centre.

